### **5.0 DOSAGE AND ADMINISTRATION**

#### **5.1 Study Drug Administration**

BMS-986205 is administered orally once day; dosing will vary 50 mg or 100 mg according to each cohort (see schema). BMS-986205 is recommended to be taken within 30 minutes after a meal. Nivolumab 240 mg is administered intravenously every 14 days (1 cycle = 14 days).

At the end of the study period, Bristol-Myers Squibb Company will not continue to supply study drug to subjects/investigators unless the Sponsor-Investigator chooses to extend their study. The investigator is responsible to ensure that the subject receives appropriate standard of care or other appropriate treatment in the independent medical judgement of the Investigator to treat the condition under study.

#### **5.2 Dose Modification and Management of Toxicity**

Measures will be taken to ensure the safety of patients participating in this trial, including the use of stringent inclusion and exclusion criteria (see Sections 4) and close monitoring (as indicated below and in the study calendar). Refer to section 5.5.

#### **5.3 Eligibility Criteria**

Eligibility criteria were selected to guard the safety of patients in this trial. Results from the nonclinical toxicology studies as well as the nonclinical/clinical data from other studies were taken into account.

#### **5.4 Monitoring**

Safety will be evaluated in this study through the monitoring of all serious and non-serious AEs, defined and graded according to NCI CTCAE V5.0. Patients will be assessed for safety (including laboratory values) according to the Study Calendar. Patients will be followed for protocol-related toxicity for 100 days following the last dose of study treatment or until receipt of another anticancer therapy, whichever comes first. General safety assessments will include serial interval histories, physical examinations, and specific laboratory studies, including serum chemistries and blood counts (see Study Calendar for the list and timing of study assessments). **All serious adverse events (SAEs) will be reported in an expedited fashion.** In addition, the investigators will review and evaluate observed AEs on a regular basis.

Patients who have an ongoing study treatment-related AE upon study completion or at discontinuation from the study will be followed until the event has resolved to baseline grade, the event is assessed by the investigator as stable, new anticancer treatment is initiated, the patient is lost to follow-up, the patient withdraws consent, or until it has been determined that study treatment or participation is not the cause of the AE.

## **5.5 Management of Adverse Events from Immunotherapy**

### **5.5.1 Dose Delay BMS-986205 and Nivolumab**

BMS-986205 and nivolumab administration should be delayed for the following:

- Grade 2 non-skin, drug-related AE, with the exception of fatigue, nausea, vomiting and anemia
- Grade 2 drug-related creatinine, AST, ALT and/or Total Bilirubin abnormalities
- Grade 3 skin, drug-related AE
- Grade 3 drug-related fatigue, nausea, vomiting, and anemia
- Grade 3 drug-related laboratory abnormality, with the following exceptions:
  - Grade 3 lymphopenia or asymptomatic amylase or lipase elevations do not require dose delay
  - Hepatic events should be managed as detailed in Section 5.5.3
- Any AE, laboratory abnormality, or intercurrent illness which, in the judgment of the investigator, warrants delaying the dose of study medication

In addition, **only BMS-986205** should be delayed for the following:

- Methemoglobin  $\geq 15\%$
- Clinically significant elevations in methemoglobin (generally 10% with a normal hemoglobin level) with any associated Grade 3 AE (hypoxia, dyspnea, confusion, etc.) attributable to sustained elevations of methemoglobin and not attributable to another etiology
- QTcF  $> 500$  msec confirmed by at least 1 repeat ECG and at least 60 msec above baseline
- If nivolumab dosing is delayed for reasons other than study drug toxicity (e.g., administrative issues, holidays, etc.), BMS-986205 dosing should continue uninterrupted

If nivolumab dosing is delayed for reasons other than study drug toxicity (e.g., administrative issues, holidays, etc.), BMS-986205 dosing should continue uninterrupted. Participants may continue to receive nivolumab during dose delays of BMS-986205 for elevations of methemoglobin and associated events, as well as QTcF prolongations.

For participants with methemoglobin elevations with associated Grade 3 AEs, if contribution of nivolumab to the associated AE cannot be ruled out (e.g., a participant with dyspnea in whom pneumonitis has not yet been ruled out), nivolumab dosing should be delayed as well. If BMS-986205 dosing is delayed, dose reduction may be necessary.

If dosing is resumed after a delay, BMS-986205 may be resumed as soon as the criteria to resume treatment are met. Nivolumab should be resumed as soon as possible after criteria to resume treatment are met but may be resumed later than BMS-986205 given the differences in each drug's administration.

Participants who require delay of any study treatment should be re-evaluated weekly or more frequently if clinically indicated and resume dosing when re-treatment criteria are met.

Tumor assessments for all subjects should continue as per protocol even if study drug dosing is delayed.

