### **5.5.3 Protocol-Specific Recommendation for Management of Hepatic Events**

Subjects with advanced HCC generally have underlying cirrhosis with decreased hepatic function. They may also have a concomitant chronic viral infection. For this study, the upper limits for inclusion were therefore adjusted to account for baseline liver dysfunction. Subjects with AST or ALT elevations within the CTCAE Grade 2 range are allowed to enroll in the study. This requires a protocol-specific approach for the management of hepatic events outlined as follows:

- Both BMS-986205 and nivolumab should be delayed for
  - Grade  $\geq 2$  toxicity in subjects with baseline AST or ALT within normal limit,
  - Grade  $\geq 3$  toxicity in subjects with baseline AST or ALT within grade 1 toxicity range
  - Drug related increase in AST or ALT at 2x baseline value or when AST or ALT is 8x ULN (whichever is lower) in subjects with baseline AST or ALT in grade 2 toxicity range.
- If AST or ALT levels do not improve with a dose delay of 3 - 5 days or if the levels worsen, initiate steroid therapy at 0.5 - 2 mg/kg/day methylprednisolone or oral equivalent.
- For ALT or AST levels  $> 8x$  ULN, initiate steroid therapy promptly at 1 - 2 mg/kg/day methylprednisolone or oral equivalent
- For all subjects initiating steroids, consult the PI within 24 hours after initiation of steroids. Gastroenterology consult is recommended.
- If AST or ALT levels do not improve within 3- 5 days or the levels worsen after the start of steroid therapy, discuss with the PI the possibility of adding mycophenolate mofetil at 1 g BID.
- Tapering of steroids can start once AST or ALT levels have declined by one CTCAE grade. Taper steroids slowly over no less than 1 month.

As outlined in above, nivolumab and BMS-986205 therapy may resume when AST or ALT have returned to patient's baseline unless the criteria for permanent discontinuation are reached. Subjects who require delay of therapy should be re-evaluated weekly or more frequently if clinically indicated. It is recommended to monitor elevations in AST or ALT approximately every 3-5 days until levels peak or begin to decline. Both therapies can be resumed when re-treatment criteria are met. The PI must be consulted prior to resuming nivolumab for all subjects who required steroid intervention. Tumor assessments for all subjects should continue as per protocol even if study drug dosing is delayed.

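### For patients entering with Grade 1 AST/ALT, Section 5.5.1 holds both drugs at a drug-related Grade 2 rise, Section 5.5.3 not before Grade 3, and the deferral to 5.5.3 does not expressly reach Grade 2

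*Combined protocol and SAP*

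**What the plan says.** Section 5.5.1 lists the events for which both drugs should be delayed. Two lines catch Grade 2 transaminase rises, and neither mentions baseline: "Grade 2 drug-related creatinine, AST, ALT and/or Total Bilirubin abnormalities", and the wider "Grade 2 non-skin, drug-related AE, with the exception of fatigue, nausea, vomiting and anemia". A later line covers "Grade 3 drug-related laboratory abnormality, with the following exceptions", and one of the items nested beneath it reads "Hepatic events should be managed as detailed in Section 5.5.3". Nothing similar is attached to either Grade 2 line.

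Section 5.5.3 explains that the entry limits were adjusted for baseline liver dysfunction and that patients with Grade 2 AST or ALT may enrol. It continues: "This requires a protocol-specific approach for the management of hepatic events outlined as follows". Both drugs are then delayed according to baseline AST/ALT:

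- normal baseline: Grade 2 or higher;
- Grade 1 baseline: Grade 3 or higher "toxicity in subjects with baseline AST or ALT within grade 1 toxicity range";
- Grade 2 baseline: a drug-related rise to 2x baseline or 8x ULN, whichever is lower.

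The same section stops treatment permanently for a drug-related AST or ALT above 10x ULN for more than 2 weeks, or above 15x ULN for any duration.

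Section 6.1.4 requires permanent discontinuation of both drugs for drug-related AST or ALT of Grade 3 or higher. A footnote lets the investigator discuss continuation with BMS. For hepatic events it refers the reader to Section 5.6.4.

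**The concern.** The delay trigger decides when treatment is withheld from patients the trial deliberately admits. The study chose its 50 mg starting dose in order to observe hepatotoxicity in HCC (Section 1.3.1), so hepatic dosing rules are central to it. Two clinicians working from different pages of the same protocol could treat the same laboratory value differently.

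The consequence is not trivial. A held patient restarts only when values return to baseline and any steroid course is complete (Sections 5.5.3 and 5.5.6). "If AST or ALT levels do not improve with a dose delay of 3 - 5 days", or if they worsen, 5.5.3 starts steroids, which are then tapered over at least a month. A patient who is not held enters none of this. Exposure to both drugs would therefore depend on which section was followed.

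The stop rule compounds the problem. Under 6.1.4 a Grade 1-baseline patient meets a default permanent stop at the same grade at which 5.5.3 first asks for a delay.

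**Working it through.** The plan gives no figure on this point to reproduce, so the check sets the rules side by side.

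**1. Are these patients in the trial?** Section 4.1 admits AST/ALT up to 5x ULN, and 5.5.3 says Grade 2 baselines are allowed. Grade 1 baselines are therefore eligible.

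**2. Delay triggers by baseline, for a drug-related rise.**

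| Baseline AST/ALT | 5.5.1 | 5.5.3 | Drug-related Grade 2 rise |
|---|---|---|---|
| Normal | Grade 2 | Grade 2 or higher | Both sections delay |
| Grade 1 | Grade 2 | Grade 3 or higher | 5.5.1 delays, 5.5.3 does not |
| Grade 2 | Grade 2 | 2x baseline or 8x ULN, whichever is lower | Framed differently; not relied on here |

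In the middle row the gap is one grade, whatever the numerical cut-offs of the grades. In the last row a mismatch arises only if a rise that stays within Grade 2 is judged drug-related.

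**3. Does the reference to 5.5.3 resolve the middle row?** It appears as an exception to the Grade 3 laboratory line. The two Grade 2 lines stand apart from it and have no exception for hepatic events. Section 5.5.6 also gives a resumption rule for Grade 2 AST/ALT without a baseline condition, so a second general section treats Grade 2 as a level at which dosing is held.

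**4. How far does the conflict reach for a Grade 1 baseline?**

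- Drug-related rise to Grade 2: the sections conflict.
- Rise not attributed to drug: the two Grade 2 lines in 5.5.1 do not apply. The Grade 1-baseline line in 5.5.3 has no drug-related condition, so it still acts at Grade 3.
- Event first seen at Grade 3, which is possible because the study calendar schedules chemistry on Day 1 of each 2-week cycle: the Grade 3 line sends it to 5.5.3, so there is no conflict over the delay.

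**5. Stop rules.** For a Grade 1 baseline, 5.5.3 treats Grade 3 as a hold, with resumption on return to baseline unless its own stop points are reached. Section 6.1.4 treats drug-related Grade 3 as a default permanent stop. Its hepatic reference does not settle the matter: 5.6 is the definition of dose-limiting toxicity and has no numbered subsections, so 5.6.4 does not exist.

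**6. What follows from a hold, if steroids are needed.** The wait before steroids is 3 to 5 days and the taper is at least 1 month, taken as 30 days. The shortest hold is then 3 + 30 = 33 to 5 + 30 = 35 days. With nivolumab every 14 days, that spans 2 or 3 scheduled infusions, depending on where the hold begins. This is the steroid path only; a patient who recovers without steroids is held for less time.

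**The case against.** The strongest reply is that the protocol already shows which section governs. The reference in 5.5.1 speaks of hepatic events without limiting them to Grade 3. Section 5.5.3 is headed as protocol-specific and gives its reason. A specific rule with a stated rationale would normally prevail over a general list. Section 5.5.1 also lets the investigator delay for any laboratory abnormality, so 5.5.3 does not force dosing through a Grade 2 rise, and Section 17.2 has every patient on active treatment discussed weekly.

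Much of this stands. A reader might infer that the protocol is silent on precedence. It is not: 5.5.3 is evidently the intended rule, and the defect is that the deferral is misplaced. A reader might also infer that literal 5.5.1 leaves the Grade 1-baseline rule with no effect at all. The documents do not support that either, because the rule still acts on rises not attributed to drug and on events first seen at Grade 3.

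The reply does not remove the Grade 2 conflict. The investigator-judgment line can add a delay but does not release one that the list already requires. Evident intent is also a weaker guide than an instruction when the contrary instruction names AST and ALT.

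On the stop rule, the footnote in 6.1.4 allows continuation after discussion with BMS, so the stop is a default and not absolute. It still differs from the stop points in 5.5.3.

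**Conclusion.** The concern holds in a limited form. For a Grade 1-baseline patient with a drug-related Grade 2 AST or ALT rise, 5.5.1 requires both drugs to be delayed and 5.5.3 does not. Read literally, 5.5.1 pre-empts the 5.5.3 threshold for those rises. Separately, 6.1.4 and 5.5.3 disagree on when raised AST/ALT ends treatment, and the reference in 6.1.4 leads nowhere.

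The size is one grade in the delay trigger. Literal 5.5.1 errs on the side of caution. The documents give neither the share of patients entering at Grade 1 nor the rate of Grade 2 rises, so the number affected is unknown. The 33 to 35 day hold is conditional on steroids and should not be read as the usual result. Alpha, power and sample size are unaffected.

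These are contradictory operative dosing rules, not missing detail. They bear on patient safety and drug exposure, and they should be corrected.

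**What to change.** Make the following changes in one amendment:

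- In 5.5.1, exempt AST and ALT from both Grade 2 lines and state that AST/ALT delays at every grade follow 5.5.3.
- Keep total bilirubin delays in 5.5.1, because the delay bullets in 5.5.3 name only AST and ALT.
- In 6.1.4, correct the hepatic reference to 5.5.3 and align the AST/ALT stop at Grade 3 or higher with the 5.5.3 stop points. The Grade 4 line in 6.1.4 also names AST and ALT and should be checked at the same time.

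The changes belong together. If the Grade 2 delay were removed while 6.1.4 stayed as it is, a Grade 1-baseline patient would go from no mandated delay at Grade 2 to a default permanent stop at Grade 3. The Grade 2 delay should therefore stay unless 6.1.4 is aligned.

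The cost is one amendment approved by BMS, the investigator and the IRB (Section 16.6). The change to 5.5.1 is wording only; the stop in 6.1.4 needs a clinical decision. Visits, data collection and sample size do not change.

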## **5.5.2 Dosage Modification**

### **5.5.2.1 Nivolumab Dose Modifications**

No dose modifications for Nivolumab are permitted

### **5.5.2.2 BMS-986205 Dose Modifications**

A dose reduction of BMS-986205 is defined as a change from a 100 mg QD tablet to a 50 mg QD tablet.

Doses of BMS-986205 should be reduced for the following AEs attributable to study therapy that do not otherwise meet criteria for discontinuation:

- Grade 3 fatigue, nausea, vomiting, or anemia related to study treatment
- Methemoglobin  $\geq 15\%$
- Clinically significant elevations in methemoglobin (generally 10%, with a normal hemoglobin level) with any associated Grade 3 AE (hypoxia, dyspnea, confusion, etc.) attributable to sustained elevations of methemoglobin and not attributable to another etiology
- QTcF  $> 500$  msec confirmed by at least 1 repeat ECG and at least 60 msec above baseline

Dose modification and interruption of BMS-986205 may occur in the setting of lower grade AEs and/or be more conservative than indicated above based on the clinical judgment of the PI. For an AE requiring dose modification, BMS-986205 should be interrupted to allow improvement of the AE, even if the AE does not otherwise meet criteria for dose delay.

Re-escalation of BMS-986205 will not be permitted once the dose of BMS-986205 has been reduced for a participant.

Only one dose reduction is permitted. The participant must discontinue study treatments if a subsequent dose reduction of BMS-986205 is required.

### **5.5.3 Protocol-Specific Recommendation for Management of Hepatic Events**

Subjects with advanced HCC generally have underlying cirrhosis with decreased hepatic function. They may also have a concomitant chronic viral infection. For this study, the upper limits for inclusion were therefore adjusted to account for baseline liver dysfunction. Subjects with AST or ALT elevations within the CTCAE Grade 2 range are allowed to enroll in the study. This requires a protocol-specific approach for the management of hepatic events outlined as follows:

- Both BMS-986205 and nivolumab should be delayed for
  - Grade  $\geq 2$  toxicity in subjects with baseline AST or ALT within normal limit,
  - Grade  $\geq 3$  toxicity in subjects with baseline AST or ALT within grade 1 toxicity range
  - Drug related increase in AST or ALT at 2x baseline value or when AST or ALT is 8x ULN (whichever is lower) in subjects with baseline AST or ALT in grade 2 toxicity range.
- If AST or ALT levels do not improve with a dose delay of 3 - 5 days or if the levels worsen, initiate steroid therapy at 0.5 - 2 mg/kg/day methylprednisolone or oral equivalent.
- For ALT or AST levels  $> 8x$  ULN, initiate steroid therapy promptly at 1 - 2 mg/kg/day methylprednisolone or oral equivalent
- For all subjects initiating steroids, consult the PI within 24 hours after initiation of steroids. Gastroenterology consult is recommended.
- If AST or ALT levels do not improve within 3- 5 days or the levels worsen after the start of steroid therapy, discuss with the PI the possibility of adding mycophenolate mofetil at 1 g BID.
- Tapering of steroids can start once AST or ALT levels have declined by one CTCAE grade. Taper steroids slowly over no less than 1 month.

As outlined in above, nivolumab and BMS-986205 therapy may resume when AST or ALT have returned to patient's baseline unless the criteria for permanent discontinuation are reached. Subjects who require delay of therapy should be re-evaluated weekly or more frequently if clinically indicated. It is recommended to monitor elevations in AST or ALT approximately every 3-5 days until levels peak or begin to decline. Both therapies can be resumed when re-treatment criteria are met. The PI must be consulted prior to resuming nivolumab for all subjects who required steroid intervention. Tumor assessments for all subjects should continue as per protocol even if study drug dosing is delayed.

- For participants with baseline up to Grade 2 AST, ALT and/or Total Bilirubin abnormalities, dosing may resume when laboratory values return to baseline and management with corticosteroids, if needed, is complete.
- Any drug-related liver function test (LFT) abnormality that meets the following criteria require discontinuation:
  - AST or ALT >10 x ULN for >2 weeks
  - AST or ALT >15 x ULN irrespective of duration
  - T. Bilirubin >8 x ULN irrespective of duration for subjects with elevated bilirubin at study entry or >5 x ULN for those with normal T bilirubin at entry
- Subjects with AST, ALT, or bilirubin values meeting discontinuation parameters should have treatment permanently discontinued.

#### **5.5.4 Management of Subjects Exhibiting Serotonin Syndrome (SS)**

The development of serotonin syndrome has been associated with exposure to another investigational agent that inhibits the IDO1 enzyme. No case of serotonin syndrome has been observed with administration of BMS-986205. Given the possibility of a class effect, there is a theoretical risk that BMS-986205 could cause an increase in serotonin levels in the brain that might trigger serotonin syndrome when administered in combination with serotonergic agents or tryptophan supplements. Use caution and monitor for symptoms of serotonin syndrome in participants receiving concurrent serotonergic psychiatric medications and/or tryptophan supplements.

This syndrome has been most closely associated with use of MAOIs, Demerol®, or linezolid; all of these agents are prohibited during the study. Selective serotonin reuptake inhibitors (SSRIs) and serotonin/norepinephrine reuptake inhibitors (SNRIs) are permitted in the study. The following procedures will be implemented if subjects exhibit the signs/symptoms of SS described in Table 1, including tremor; hyperreflexia; and spontaneous, ocular, or inducible clonus, together with agitation, fever, diaphoresis, or muscle rigidity:

- Immediately discontinue BMS-986205 administration. Administration of other study drugs may continue.
- Immediately interrupt any SSRI or SNRI administration.
- Provide appropriate medical management of the subject until all signs/symptoms are resolved (e.g., IV fluids and/or sympathomimetic amines for hypotension, benzodiazepines for agitation, administration of 5-hydroxytryptamine antagonists, such as cyproheptadine).

- If subject chooses to withdraw from the study or must restart treatment with SSRI or SNRI, the subject should be scheduled for a follow-up visit. Treatment with SSRI or SNRI may be initiated 2 weeks after resolution of signs and symptoms of SS.

**Table 1. Signs and Symptoms of Serotonin Syndrome**

Tremor and hyperreflexia
Spontaneous clonus
Muscle rigidity, temperature > 38°C (100.4°F), and either ocular clonus or inducible clonus
Ocular clonus and either agitation or diaphoresis
Inducible clonus and either agitation or diaphoresis

**5.5.5 Treatment of Methemoglobinemia Associated with BMS-986205****5.5.5.1 Detection**

BMS-986205 may produce a p-chloroaniline metabolite. P-chloroaniline has been associated with the production of methemoglobin. Symptoms of methemoglobinemia are related to the lack of oxygen delivery to tissues and are proportional to the fraction of methemoglobin, as described below for participants with normal hemoglobin levels.

Symptoms associated with elevations of methemoglobin are as follows:

0% to 10%	Usually asymptomatic
10% to 20%	Cyanosis without other symptoms
20% to 50%	Headache, dyspnea, lightheadedness (possibly syncope), weakness, confusion, palpitations, chest pain
50% to 70%	Coma, seizures, arrhythmias; acidosis
> 70%	Usually death

Note that participants with anemia may experience symptoms at lower methemoglobin percentages than listed above, depending on the degree of anemia.

Increasing levels of methemoglobin may confound the results of standard pulse oximeters, with values of around 85% reported consistently as methemoglobin levels increase, regardless of the true oxygen saturation.

When methemoglobinemia is suspected, part of the diagnostic work-up includes evaluation for other disorders that can present with a similar clinical picture, including cardiac and pulmonary disease. A fresh peripheral blood sample (either venous or arterial) should be sent for evaluation of methemoglobin levels; methemoglobin levels may vary with storage of blood. Testing is done at Screening, each treatment cycle, or more frequently if clinically indicated based on symptoms.

